8.1.3 Other Endpoints and Assessments

The following analyses will also be performed as defined in the referenced sections using descriptive statistics:

- Additional Safety Endpoints (**Section 3.5.1**)
- Additional Effectiveness Endpoints (**Section 3.5.2**)
- Procedural Assessments (**Section 3.5.3**)
- Quality of Life Assessments (**Section 3.5.4**)

8.2 General Statistical Methods

8.2.1 Analysis Sets

All Attempt and Treatment Subjects will be used for the primary safety endpoint and additional safety endpoint analyses, unless otherwise specified. All LUX-Dx monitored Treatment Subjects will be used for the primary effectiveness endpoint and additional effectiveness endpoint analyses, unless otherwise specified. Subjects who do not receive a LUX-Dx device or do not establish a LATITUDE Clarity connection by the end of the effectiveness evaluation period will not be included in the main effectiveness endpoints. Effectiveness endpoints will be summarized separately for these subjects as binary rates or a listing.

Endpoint data will be summarized separately for Roll-In Subjects. Roll-In Subjects will not be used in the main endpoint analyses.

8.2.2 Control of Systematic Error / Bias

Control and reduction of potential bias associated with a single-arm study design have been addressed by a series of measures including but not limited to:

- Patients meeting the eligibility criteria and signing the ICF will be eligible for sequential enrollment in the study.
- ECG recurrence data for Non-Roll-In Treatment subjects reported by the site from 12-Lead ECGs will be evaluated by a third-party Arrhythmia Core Laboratory according to standardized protocols.
- LUX-Dx episodes will be adjudicated to verify recurrence meeting the definition of Detectable AF, AFL or AT.
- Cardiac MRI / CT images utilized for assessing potential PV stenosis will be evaluated by a third-party Cardiac Imaging Core Laboratory according to standardized protocols.
- The use of a comprehensive set of study procedures as defined in the protocol which ensure consistent patient management.
- Comprehensive site and data monitoring to ensure accurate and complete recording of study data.
- The use of an independent Clinical Events Committee (Phase 1 Protocol **Section 19.2** Error! Reference source not found.) will review and adjudicate all potential SAEs and primary safety outcomes.
- Creation of a complete Clinical Study Report and full dataset to allow scientific and clinical reviewers to independently assess potential error and bias.
- To avoid any center effect and bias, no center will be authorized to enroll more than 33 Treatment Subjects (13% of the total planned enrollment of 258 Treatment Subjects).

8.2.3 Study Success and Control of Type I Error

The Primary Safety Endpoint and Primary Effectiveness Endpoint must pass in order to achieve study success. Both primary endpoints will be tested at a significance level of 2.5% while still maintaining the overall Type I error level at no greater than 2.5%. This follows the methodology of the Intersection-Union Test (IUT).

8.3 Data Analyses

8.3.1 Roll-In Subject Analyses

The stipulated analyses for Roll-In Subjects will be summarized with descriptive statistics. Endpoint data for Roll-In Subjects will be summarized but no hypothesis testing, subgroups, tipping point, or multivariate analyses will be performed. Recurrence data from 12-Lead ECGs for Roll-in subjects will not be evaluated by a third-party. Site assessment of the rhythm found on the 12-Lead ECG will be captured in the EDC system and used to identify recurrence of AF, AFL, or AT for effectiveness endpoint evaluations.

8.3.2 Interim Analyses

No formal interim analyses are planned for the purpose of stopping the study early for declaring success or futility. Analysis of each endpoint will be performed for regulatory submission when all

applicable data for that endpoint has been collected or based on specific geographic requirements Error! Bookmark not defined.. The ADVANTAGE AF Study may be used to satisfy the requirements of multiple regulatory bodies. Details on these analyses will be included in the ADVANTAGE AF SAP when available.

8.3.3 Sensitivity Analyses

8.3.3.1 Sensitivity to Missing Data

Tipping point analyses will be performed for the PSE and PEE to evaluate the impact of missing data due to subjects exiting the study prior to the Day 90 Assessment for the PSE or prior to the Day 360 Assessment for the PEE.

8.3.3.2 Sensitivity of Effectiveness to Other Ablations in the Left Atrium

The impact of allowing ablation in the left atrium for concomitant arrhythmias (when deemed clinically necessary) without constituting Acute Procedural Failure will be assessed for the PEE. The PEE will be calculated counting subjects who received said ablations (excluding ablation of an accessory pathway or atypical AVNRT) as Treatment Failures.

8.3.3.3 Sensitivity of Effectiveness to Amiodarone Use Post Ablation Procedure

The impact of allowing Amiodarone use to the end of the blanking period without constituting Chronic Treatment Failure will be assessed for the PEE. The PEE will be calculated counting subjects with Amiodarone use beyond 30 days after the Index Ablation Procedure as Treatment Failures.

8.3.3.4 Sensitivity of Effectiveness to the timing of AAD discontinuation

The impact of allowing the use of Non-failed Class I/III AADs and Amiodarone through the Day 90 Assessment (or Day 104 when Day 90 Assessment is completed late or missed) without constituting Chronic Treatment Failure will be assessed for the PEE. The PEE will be calculated counting subjects with any Non-Failed Class I/III AAD or Amiodarone use after the blanking period as Treatment Failures.

8.3.3.5 Sensitivity of Effectiveness to the timing of Day 360 Assessment

For the PEE, if the Day 360 Assessment is completed late (after Day 390) only events that occurred within window count as Treatment Failures, as described in Appendix A of the ADVANTAGE AF SAP. In this sensitivity analysis, the PEE will be calculated counting events that occur outside of the visit window (after Day 390) as Treatment Failures.

8.3.3.6 Sensitivity of Effectiveness to AT/AFL Detection Method (Tipping Point Analysis)

A tipping point analysis will be performed for the PEE to assess the impact of using the LUX-Dx AT algorithm with a minimum duration setting of 4 hours to detect AT and AFL events. All Treatment subjects with PEE Success will be one by one considered to have had an undetected AT/AFL event counting as a PEE failure. The number of subjects that would need to have had an undetected AT/AFL event to fail the PEE will be considered the tipping point. The probability of the tipping point occurring will be calculated based on the rate of PEE Failures observed in ADVANTAGE AF Phase 1 that were due to AT or AFL recurrence recorded by Holter or Event Monitor with no other mode of failure. Additional details for this analysis will be included in the Statistical Analysis Plan.

8.3.3.7 Sensitivity of Effectiveness to LUX-Dx S-ECG Storage

The impact of the LUX-Dx S-ECG storage capacity on the determination of Detectable AF, AFL, and AT will be assessed for the PEE. LUX-Dx detected AT and AF episodes or patient-triggered symptomatic episodes without a stored S-ECG will be considered to have confirmed AF, AFL, or AT and included in the determination of Detectable AF, AFL, and AT.

8.3.4 Subgroup Analyses

Analyses will be performed to evaluate whether any significantly different effects exist in the Primary Safety Endpoint or Primary Effectiveness Endpoint within subgroups of subjects. The list of covariates (with applicable subgroups in parentheses) will include at least the following:

- Subject demographics (e.g., age-[e.g. age >=65 vs. <65, Medicare eligible], gender)
- Subject baseline characteristics (e.g., LVEF, cardioversion history, BMI, LA diameter, and years since AF diagnosis)
- Index Procedure lesion sets
 - PV + LAPW ablation alone versus PV + LAPW plus additional ablations
 - CTI ablation versus no CTI ablation
- Operator learning curve (e.g. number of prior procedures completed by operator at time of procedure, counting at a minimum, the procedures from ADVANTAGE AF Phase 1 and Phase 2)
- Mapping of the PW during Index Procedure

Additional covariates for the Primary Effectiveness Endpoint only include:

- Amiodarone use post Index Procedure versus no Amiodarone use post Index Procedure.
- LUX-Dx model (LUX-Dx II+ [M312] vs LUX-Dx [M301] or LUX-Dx II [M302])

Each subgroup covariate will be included as a single independent variable in a logistic regression model with the endpoint outcome as the dependent variable and a test for significance at the 15% level will be performed.

In addition to subgroup analyses, descriptive statistics of subject demographic and baseline characteristics will be presented for each subgroup listed in this section.

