	
 • Death • Cardiac tamponade / perforation • Pericarditis • Any PFA system related or PFA procedure-related cardiovascular or pulmonary adverse event 	Day 0 – Day 30
The CSAE components of the PSE are defined in Table 3.3-2 .		
ADDITIONAL SAFETY ENDPOINTS	
 • Primary Safety Endpoint Through Day 360 Assessment • Composite Non-Serious Adverse Event • Related AEs • Any SAE • Post-Blanking Arrhythmia Hospitalizations • Post-Blanking Cardioversions • Coronary Spasm Events • Adverse Effects of Intraprocedural Administration of Nitroglycerin 	

A Prospective Single Arm Open Label Study of the FARAPULSE Pulsed Field Ablation System in Subjects with Persistent Atrial Fibrillation
 
The ADVANTAGE AF Study – Phase 2
	
PRIMARY EFFECTIVENESS ENDPOINT	
The primary effectiveness endpoint (PEE) is the proportion of LUX-Dx monitored Treatment Subjects with Treatment Success through the Day 360 Assessment.
 
Treatment Success is defined as:
 
 1. Persistent AF Acute Procedural Success AND 2. Persistent AF Chronic Success, defined as freedom from the following after the Blanking Period (excluding documented CTI-dependent flutter if subject was not treated with the FARAPPOINT PFA Catheter): 
 i. Arrhythmia: Occurrence of any Detectable AF, AFL or AT ii. Re-ablation: Any re-ablation for AF, AFL or AT iii. Cardioversion: Any electrical cardioversion for AF, AFL or AT iv. AAD Use: Use of a Non-Failed Class I / III AAD or amiodarone.
ADDITIONAL EFFECTIVENESS ENDPOINTS	
 • CTI-Mediated AFL Treatment Success • Re-Ablation Rate for CTI-Mediated AFL • Persistent AF Acute Procedural Success • Persistent AF Chronic Success • Freedom from Detectable AF, AFL, AT • Freedom from Symptomatic Recurrence and Intervention to Treat AF, AFL, or AT • Single Procedure Treatment Success • Off Drug Treatment Success • Re-Ablation Rate • AF, AFL, and AT Burden • Healthcare Utilization by AF, AFL, and AT Burden • Healthcare Utilization by AF, AFL, or AT Recurrence Duration
PROCEDURAL ASSESSMENTS	
Assessments of procedure durations
 
 • Procedure Time • LA Dwell Time • PVI and PWI Ablation Time • CTI Ablation Time • Fluoroscopy Time 
Characterization of lesion sets
 
 • PVI Ablations • PWI Ablations • CTI Ablations • Other Ablations

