1.2 FARAPoint Pulsed Field Ablation Catheter

An additional catheter included in the ADVANTAGE AF Phase 2 Study is the FARAPoint PFA Catheter, which is designed for ablation of the cavotricuspid isthmus (CTI).

Initial data on the safety and feasibility of the FARAPoint Catheter has been collected in twenty subjects in the PersAFOne II Study. In this study subjects undergoing ablation for PersAF using the FARAWAVE Catheter for PVI and Left Atrium Posterior Wall (LAPW) ablation also received ablation of the CTI using the FARAPoint Catheter delivering two applications per site at 2000V. Study follow-up included an invasive electrophysiological remapping procedure to assess index treatment durability at 60 days post-index procedure.

No primary safety events were reported in any subjects. Two SAEs (pericardial effusion) have been reported in two subjects during study follow-up during required remapping procedures. Neither was deemed related to the FARAPULSE PFA devices or ablation procedure. All subjects had successful acute CTI ablation as determined by electrophysiological assessment of bidirectional block across the cavotricuspid isthmus. As reported in the interim progress report, dated 02-Feb-2022, 17 subjects had undergone the protocol-specified re-mapping procedures. Among these, bidirectional isthmus block remained in 14 of the 17 subjects (82.4%).¹⁷

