4.1.2 Number of ADVANTAGE Phase 2 Subjects

Approximately 338 treated subjects will be enrolled in Phase 2 of the ADVANTAGE AF study (up to 80 Roll-In Subjects and approximately 258 Treatment Subjects) after enrollments in Phase 1 of the study are complete. Subjects participating in Phase 1 cannot be approached for participation in Phase 2 for treatment with the FARAPoint Catheter.

Roll-In Subjects (up to 80): The first subject enrolled by each ablating Investigator at each site will be treated with the investigational devices as part of Investigator preparation, up to a maximum of 80 subjects across 40 investigational sites. Subjects will be pre-screened prior to enrollment to ensure the criteria for CTI ablation will be met and the FARAPoint PFA Catheter is utilized. Roll-In procedures may be adapted based on prior experience, or additional subjects may be required as described further in **Section 4.2**.

Treatment Subjects (258): A planned 258 Treatment Subjects will be enrolled to support the Primary Safety Endpoint. No site may enroll more than 33 Treatment Subjects (13% of those planned). Subject enrollment will stop once approximately 258 Treatment Subjects are accrued. It is expected

that approximately 30% of the Treatment subjects will be treated with the FARAPoint PFA Catheter for CTI-mediated AFL. Enrollments may be controlled to ensure an estimated 80 subjects are treated with the FARAPoint PFA Catheter. There is no predetermined upper limit for the number of Treatment subjects receiving CTI ablation with the FARAPoint PFA Catheter, therefore the FARAPoint- treated subjects may exceed 80 when the total number of 258 Treatment subjects are accrued.

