8.3.7 Multivariable Analyses

For the Primary Safety Endpoint and Primary Effectiveness Endpoint, univariable analyses of the following covariates will be performed, and any found to be significantly associated with the outcome at the 0.15 alpha level will be included as covariates in a multivariable regression model. Backward selection with 0.15 alpha level stay criterion will be used to determine the final multivariable model.

The list of baseline covariates includes, but is not necessarily limited to:

- Subject demographics (e.g., age, gender)
- Subject baseline characteristics (e.g., LVEF, cardioversion history, BMI, LA diameter, and years since AF diagnosis)
- Index Procedure lesion sets
 - PVI + LAPW ablation alone versus PVI + LAPW plus additional ablations
 - CTI ablation versus no CTI ablation
- Operator learning curve (e.g., number of prior procedures completed by operator at time of procedure, counting at a minimum, the procedures from ADVANTAGE AF Phase 1 and Phase 2)
- Mapping of the PW during Index Procedure

Additional covariates for the Primary Effectiveness Endpoint only include:

- Amiodarone use post Index Procedure versus no Amiodarone use post Index Procedure
- LUX-Dx model (LUX-Dx II+ [M312] vs LUX-Dx [M301] or LUX-Dx II [M302])

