Detectable AF, AFL, or AT	
Detectable AF, AFL or AT is an episode of AF, AFL or AT which:
 
 • Is recorded for review on a LUX-Dx ICM and meets any of the following criteria: 
 ○ Adjudicated symptomatic (patient initiated) recording that contains ≥ 30 seconds of continuous atrial arrhythmia. ○ Adjudicated AF or AT episode captured by LUX-Dx that contains at least 30 seconds of atrial arrhythmia and overlaps a simulated bi-monthly, 2 minute event monitor transmission period. ○ Adjudicated AF or AT episode captured by LUX-Dx that contains at least 30 seconds of atrial arrhythmia and overlaps a simulated 24 hour holter period occurring the day before the Day 180 and Day 360 Assessments (or last day of respective visit window if visit(s) is missed)⁸. • Continuous AF, AFL or AT for the entirety of a 12 lead ECG if the continuous interpretable signal is 10 seconds or longer • Exclusions: 
 ○ CTI isthmus-dependent AFL if the subject did not have a CTI ablation with the FARAPoint PFA Catheter ○ Arrhythmias recorded on other devices, including implantable monitors and consumer wearables, not specified in the ADVANTAGE AF Study procedures
Failed AAD	
Failed AADs include any and all Class I / III AAD determined at the time of enrollment to have been failed for effectiveness or intolerance. Failed AADs do not include Class I / III AADs determined at the time of enrollment solely to be contraindicated.
 
Failed AADs must be established as part of the Baseline Assessment for agent, type of failure (arrhythmia recurrence or AAD intolerance) and the maximum failed dose (the total daily dose at which such failure occurred).

Intent Subjects	
Intent Subjects are defined in Section 6.6.3 of the ADVANTAGE Phase 1 Protocol.

Non-Failed AAD	
A Non-Failed AAD is:
 
 • Any Class I / III AAD not established at the Baseline Assessment as a Failed AAD • Any Failed AAD used after Day 90 at a daily dose exceeding the maximum failed dose established at the Baseline Assessment

⁸ Day prior to the Day 180 and Day 360 visits was selected to prevent overlap in the rhythm captured by the visit-required 12-lead ECG.

Term	Definition
Persistent atrial fibrillation	PersAF is defined as continuous AF that is sustained beyond 7 days, but not greater than 12 months duration.

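### The Phase 2 effectiveness comparison of CTI ablation versus no CTI ablation is biased towards lower success with CTI ablation, because CTI-dependent flutter counts as failure only after FARAPOINT ablation

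*Combined protocol and SAP*

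**What the plan says.** Appendix A 8.3.4 sets the purpose: "Analyses will be performed to evaluate whether any significantly different effects exist in the Primary Safety Endpoint or Primary Effectiveness Endpoint within subgroups of subjects". Among the lesion-set covariates it lists "CTI ablation versus no CTI ablation", and PV plus posterior wall ablation alone against the same with additional ablations. Each covariate enters a logistic model alone, and "a test for significance at the 15% level will be performed". Appendix A 8.3.7 repeats both covariates for the multivariable model, where "any found to be significantly associated with the outcome at the 0.15 alpha level will be included as covariates in a multivariable regression model".

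The endpoint definition treats the two groups differently. The Phase 2 synopsis defines chronic success as "excluding documented CTI-dependent flutter if subject was not treated with the FARAPPOINT PFA Catheter". The definition of Detectable AF, AFL, or AT in Appendix A 23.2 lists as an exclusion "CTI isthmus-dependent AFL if the subject did not have a CTI ablation with the FARAPoint PFA Catheter". The footnote to Appendix A 3.4.2 extends the rule to re-ablation and cardioversion for CTI-dependent flutter, and says outright that these are failures in ablated subjects. That footnote names the FARAPULSE PFA Catheter, where the other two places name FARAPOINT.

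Appendix A 7.7.2.5 assigns index CTI ablation to FARAPOINT, so the covariate and the switch in the failure rule nearly coincide. On numbers, Appendix A 4.1.2 expects that "approximately 30% of the Treatment subjects will be treated with the FARAPoint PFA Catheter for CTI-mediated AFL", and allows enrollment to be controlled to reach an estimated 80 of 258.

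**The concern.** The two levels of the covariate are scored on different outcomes. One level carries a failure mode that the other cannot have. With identical rhythm outcomes in both groups, the rule alone lowers success in the CTI-ablated group. Covariate adjustment in 8.3.7 cannot correct this, because the fault lies in the outcome.

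In Phase 1 the same covariate (8.3.3 and 8.3.5) was coherent, since 3.3.2 and 23.2 of the main protocol exclude CTI-dependent flutter for every subject. Phase 2 changed the endpoint and kept the covariate.

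Nothing else in Appendix A repairs it. The sensitivity analyses 8.3.3.1 to 8.3.3.7 cover missing data, left atrial ablations, amiodarone, timing of drug discontinuation, late Day 360 visits, AT/AFL detection and S-ECG storage. None rescores flutter. In 3.5.2, freedom from detectable arrhythmia uses the 23.2 definition and so inherits the split rule, and the CTI-specific endpoints cover only FARAPOINT subjects and have no comparator.

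At stake is interpretation. Appendix A 3.1 says that Phase 2 seeks approval of adjunctive FARAPOINT use. As planned, a significant CTI result could not be told apart from a scoring artefact.

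**Working it through.** **The plan's own figure.** Appendix A gives no sample size or power for this contrast. Its PEE figure does reproduce. With 55% against a goal of 40%, one-sided 0.025 and exact binomial, n = 122 requires at least 60 successes (attained alpha 0.0248, power 91.6% against the stated 90%). With 10% attrition, 122 / 0.9 = 135.6, which rounds up to 136. This confirms 55% as the planning rate. The point made here does not change it.

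**Inputs for the contrast.**
- Group sizes: 80 FARAPOINT subjects and 258 - 80 = 178 others (Appendix A 4.1.2). The 30% expectation gives 0.30 x 258 = 77, which is consistent.
- Success under a common rule: 55% in both groups, meaning no true difference.
- Test: 15% level, taken as two-sided because 8.3.4 does not say. Critical value 1.44.
- q: the share of would-be successes in the FARAPOINT group whose only failure is documented CTI-dependent flutter. The documents do not give it. The assumed range is 2% to 10%. As a ceiling I use 3/17 = 17.6%, the share that had lost CTI block at remapping in the feasibility study (Appendix A 1.2).

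**Formulas.** Success in the CTI group as scored is p1 = 0.55(1 - q), so the built-in gap is 0.55q. The standard error is SE = sqrt[p1(1 - p1)/80 + 0.55 x 0.45/178]. With d = (p1 - 0.55)/SE, the chance of a flag is Phi(d - 1.44) + Phi(-d - 1.44). This is the Wald approximation to the single-covariate logistic test.

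**Example, q = 10%.** p1 = 0.495, SE = sqrt(0.003125 + 0.001390) = 0.0672, and d = -0.055/0.0672 = -0.82. The chance of a flag is Phi(-2.26) + Phi(-0.62) = 0.012 + 0.267 = 0.279.

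| q | CTI-group success | Gap (points) | Odds ratio | Flag at 15% level | Flag with CTI worse |
|---|---|---|---|---|---|
| 0 | 55.0% | 0 | 1.00 | 15% | 7.5% |
| 2% | 53.9% | 1.1 | 0.96 | 15.5% | 10.1% |
| 5% | 52.3% | 2.75 | 0.90 | 18.4% | 15.2% |
| 10% | 49.5% | 5.5 | 0.80 | 27.9% | 26.7% |
| 17.6% (ceiling) | 45.3% | 9.7 | 0.68 | 50.4% | 50.2% |

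With 10% attrition (72 versus 160), the flag rates at q = 2%, 10% and 17.6% are 15.5%, 26.7% and 47.5%. At q = 2% the total barely moves, but about two thirds of flags (10.1/15.5) already point against CTI ablation, compared with half when q = 0.

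**The case against.** Several points on the other side are sound.

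- **Indication.** Appendix A 7.7.2.5 requires CTI ablation in subjects with a history of typical flutter or flutter during the procedure. The groups differ before any scoring rule applies, and rescoring does not remove that. A reader might infer that CTI ablation must look worse by definition. The documents do not support this: the rule pushes in one direction, but selection and true effects can move the observed difference either way.
- **Detection.** Only documented CTI-dependent flutter is treated differently, and flutter never shown to be CTI-dependent counts in both groups. The adjudication software in 23.2 separates atrial from non-atrial arrhythmia and does not identify isthmus dependence. AFL recurrences reported at follow-up need a 12-lead ECG for core laboratory adjudication. The initial LUX-Dx setting for AT is 4 hours at 110 bpm (7.6), and asymptomatic episodes count only if they overlap sparse simulated windows (8.1.2.3). A first re-ablation within blanking is not a failure (7.14.1). All of this favours the low end of the range.
- **Large gaps.** A reader might suppose a gap of ten points. That needs q = 10/55 = 18.2%, slightly above the entire 3/17 reconnection rate. Reconnection is not the same as flutter being the only failure, so the ceiling is not an estimate, and it comes from 17 subjects.
- **Consequence.** Study success rests on the two primary endpoints (8.2.3). The subgroup tests are exploratory. With about 13 named PEE covariates each tested at 15%, roughly 13 x 0.15 = 2 chance flags are expected anyway.
- **Partial help elsewhere.** The CTI endpoints in 3.5.2 show how much flutter recurs in FARAPOINT subjects, which helps in reading a flag. They do not rescore the PEE.

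Counting flutter as failure after FARAPOINT ablation may well be intended for the primary endpoint. That does not make it a fair yardstick between ablated and non-ablated subjects. It is also fair that a rescored row no longer tests the PEE exactly as defined, so the as-defined row should stay beside it. The separate Phase 2 SAP that Appendix A cites (8.3.8, 11.2) is not in the supplied text, so a common rule set there cannot be ruled out.

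**Conclusion.** The point holds in a limited form. On the text of Appendix A, the PEE contrast by CTI ablation in 8.3.4 and 8.3.7 has a built-in bias against CTI ablation. The direction follows from the rule. The size does not, because it depends on an unstated share of subjects who fail only through documented CTI flutter. For an assumed 2-10% of would-be successes, the gap is about 1 to 5.5 points (odds ratio 0.96 to 0.80), and the flag rate is about 15.5% to 28% instead of 15%. About 50% is an upper bound that takes the 3/17 reconnection rate as a ceiling. These figures assume 80 versus 178 subjects, 55% success under a common rule and a two-sided test.

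The additional-ablations covariate is affected only to the extent that CTI ablation counts as additional, since other permitted ablations also fall there. The primary safety comparison on the same covariate and the primary PEE test are untouched. A reader should not conclude that the primary result is biased.

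**What to change.** For the two lesion-set covariates in Appendix A 8.3.4 and 8.3.7, keep the row for the PEE as defined. Add a row with the PEE scored under one rule for everyone: documented CTI-dependent flutter, and re-ablation or cardioversion for it, excluded in all subjects as in Phase 1. Base interpretation and entry into the multivariable model on the common-rule version. Leave the primary PEE unchanged, report CTI-flutter recurrence through the CTI endpoints in 3.5.2, and state that the contrast remains non-randomised, with CTI ablation given by indication. Reconcile the catheter named in the footnote to 3.4.2 with the synopsis and 23.2.

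The cost is SAP wording and one derived outcome variable, with no new data. The downside is that two rows use a slightly different outcome from the primary PEE and need a footnote.

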3.4.2 Persistent AF Chronic Success

Persistent AF Chronic Success is defined as freedom from any of the following through the Day 360 Assessment after the Blanking Period, excluding documented CTI-dependent AFL¹:

- a. **Arrhythmia:** Occurrence of any Detectable AF, AFL or AT
- b. **Re-ablation:** Any re-ablation for AF, AFL or AT
- c. **Cardioversion:** Any electrical cardioversion for AF, AFL or AT
- d. **AAD Use:** Use of a Non-Failed Class I / III AAD or amiodarone

Within the Blanking Period, recurrent arrhythmias can be managed with AADs, cardioversion or one re-ablation procedure with the FARAPULSE PFA System without constituting Persistent AF Chronic Failure. Titration of Class I/III antiarrhythmic medications are allowed during the Blanking Period. Subjects are allowed to remain on Class I/III antiarrhythmic medications at the historic maximum ineffective dose (prior to the ablation procedure) after the 90-day Blanking Period, except amiodarone. Subjects that undergo more than one re-ablation procedure within the Blanking Period will be classified as a Persistent AF Chronic Failure. Complete definitions of the endpoint terms (including Blanking Period, Detectable AF, AFL, or AT, Failed AAD and Non-Failed AAD), can be found in **Section 23.2**.

¹ Post-blanking CTI-dependent AFL or re-ablation or cardioversion for CTI-dependent AFL does not constitute Treatment Failure if the subject did not have a CTI ablation with the FARAPULSE PFA Catheter but will be a Treatment Failure if the subject did receive ablation with the FARAPULSE PFA Catheter.

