7.4 Antiarrhythmic Drugs

Use of Class I / III AADs during the ADVANTAGE AF Study must be managed carefully.

The terms “Antiarrhythmic Drugs, Class I and III”, “Blanking Period”, “Failed AAD” and “Non-Failed AAD” are defined specifically in **Section 23.2**.

Failed AADs

At the Baseline Assessment, **Section 7.5**, all Class I and III AADs previously used by the subject must be defined as Failed AADs or Non-Failed AADs in the CRF, including for any Failed AADs the maximum failed dose (see **Section 23.2**).

Amiodarone

- May not be used after the Blanking Period or the subject becomes a Treatment Failure.
- If subjects are prescribed Amiodarone, treatment must be stopped by the Day 30 Assessment.

Managing AADs During the Blanking Period

During the Blanking Period the subject should be assessed for AAD continuation. Titration of Class I / III AADs is allowed during the Blanking Period.

To account for the hard cutoff of the Blanking Period at 90 days and given the permitted visit window for the Day 90 Assessment (90 ± 14 days), AADs that are taken during the Blanking Period but are stopped at the time of a within-window Day 90 visit (up to and including Day 104) will not be counted as potential Treatment Failures to allow the necessary physician evaluation.

Managing AADs After the Blanking Period

If indicated, subjects may remain on Class I / III AADs following the Blanking Period, preferably those established as Failed AADs (see **Section 23.2**) at or below the maximum failed dose so as not to create a post-Blanking Period Treatment Failure.

Use of a Non-Failed AAD after the Day 90 Assessment constitutes a Treatment Failure for the primary effectiveness endpoint.

AAD Monitoring

At all subsequent follow-up assessments, subject compliance with, and changes in drugs and daily doses for any Class I / III AAD, will be elicited and recorded.

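### The Phase 2 amiodarone covariate has no end date, so it overlaps with the effectiveness outcome and its coefficient is biased toward harm if any subject uses the drug after blanking

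*Combined protocol and SAP*

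**What the plan says.** Appendix A 8.3.4 (Subgroup Analyses) and 8.3.7 (Multivariable Analyses) each add, for the PEE only, the contrast "Amiodarone use post Index Procedure versus no Amiodarone use post Index Procedure". Neither section says when the exposure window closes. In 8.3.4, "Each subgroup covariate will be included as a single independent variable in a logistic regression model", tested at the 15% level. In 8.3.7 a covariate enters at 0.15 and stays under backward selection at 0.15. That list opens with "The list of baseline covariates includes, but is not necessarily limited to".

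The outcome in these models also contains amiodarone. Section 3.4.2(d) lists "Use of a Non-Failed Class I / III AAD or amiodarone" among the events that end Chronic Success, and 7.4 says of amiodarone: "May not be used after the Blanking Period or the subject becomes a Treatment Failure".

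Use before that point is handled differently. Section 7.4 states "If subjects are prescribed Amiodarone, treatment must be stopped by the Day 30 Assessment". Sections 8.3.3.3 and 8.3.3.4 confirm that use within blanking, and up to the Day 90 Assessment (Day 104 if that visit is late or missed), is not a failure in the main PEE analysis.

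**The concern.** A subject with any post-blanking amiodarone is in the exposed group and is also a failure. There are two routes, and they should be kept apart.

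- **Continuers.** An early user who stays on amiodarone past the allowed period fails by definition. Here the covariate contains part of the outcome.
- **Late starters.** A subject recurs after blanking, has therefore already failed on arrhythmia, and is then given amiodarone. The drug adds nothing to the outcome, but it moves that failure from the unexposed to the exposed group. This is reverse causation. The Day 30 stopping instruction concerns early use and does not limit it.

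Both routes push the coefficient toward harm. The question such a covariate can usefully address is whether amiodarone carried into early follow-up supports the success rate, in which case users would look better. The coding works against seeing that. If the variable is retained in 8.3.7, it may also shift the other adjusted coefficients; I have not quantified that effect.

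**Working it through.** **The plan's own figure.** The documents give no number for this covariate. The related figure is the PEE sample size, which supplies the outcome rate. The exact binomial test with n = 122, rejecting at 60 or more successes, has one-sided alpha 0.0248 under 40% and power 0.916 under 55%. The plan states 0.025 and 90%. Attrition: 122 / 0.9 = 135.6, so 136, as stated. The expected failure rate is 1 − 0.55 = 0.45.

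**Late starters.** Inputs: 45% failure in everyone (from the plan); N = 230 monitored subjects (assumed; 258 planned less 10% is about 232); 15% early users with no drug effect (assumed); k failures without early use who receive amiodarone after blanking (assumed).

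- Early users: 0.15 × 230 = 34.5, giving 15.5 failures and 19.0 successes.
- Others: 195.5, giving 88.0 failures and 107.5 successes.
- Moving k failures into the exposed group: OR(k) = [(15.5 + k) × 107.5] / [19.0 × (88.0 − k)].
- Standard error of log OR: square root of the sum of the reciprocals of the four cells.

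| k | OR | Wald p |
|---|---|---|
| 0 | 1.00 | – |
| 5 | 1.40 | 0.34 |
| 10 | 1.85 | 0.07 |
| 15 | 2.37 | 0.009 |

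At k = 10 the failure rate is 25.5 / 44.5 = 57% in users and 78.0 / 185.5 = 42% in non-users, although the drug does nothing. On these inputs the 0.15 threshold is crossed at about k = 8 (p about 0.14; k = 7 gives about 0.19).

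**Continuers.** Let q be the share of users who continue past the allowed period. With no drug effect, the failure rate in users is q + (1 − q) × 0.45, against 0.45 in non-users. At q = 10% this is 0.505, so OR = (0.505 / 0.495) / (0.45 / 0.55) = 1.25. The probability of a result toward harm with p < 0.15 comes from exact enumeration of the likelihood-ratio test, with N = 258 and 20% users (assumed):

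| q | OR | P(p < 0.15, toward harm) |
|---|---|---|
| 0 | 1.00 | 7% |
| 5% | 1.12 | 14% |
| 10% | 1.25 | 23% |
| 20% | 1.56 | 49% |
| 30% | 1.95 | 75% |

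With the share of users varied from 10% to 30%, the probability at q = 10% runs from 19% to 27%, and at q = 30% from 57% to 85%.

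**Masking.** If amiodarone truly had a favourable OR of 0.7, the failure rate in users who stop in time would be 0.364. Solving q + (1 − q) × 0.364 = 0.45 gives q = 0.086 / 0.636, about 13.5%. At that share of continuers the observed OR is 1.0.

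**The case against.** Much of the case on the other side stands. Most post-procedure amiodarone may be early use, which is not a failure, and 7.4 calls for stopping by the Day 30 Assessment. A reader might infer that amiodarone will look harmful by construction, or that the variable will probably be retained at 0.15. The documents support neither. If nobody uses the drug after blanking there is no forced bias, at 5% continuing the OR is only about 1.1, and with 5 late-rescued failures p is about 0.34. The numbers of users, continuers and rescued subjects are not given.

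The dependence of success on amiodarone is also examined elsewhere. Section 8.3.3.3 begins "The impact of allowing Amiodarone use to the end of the blanking period without constituting Chronic Treatment Failure will be assessed for the PEE" and recounts use beyond 30 days as failure. Section 8.3.3.4 begins "The impact of allowing the use of Non-failed Class I/III AADs and Amiodarone through the Day 90 Assessment" and recounts any use after blanking as failure. Off Drug Treatment Success in 3.5.2 counts any Class I/III drug after Day 90 as failure. These are real safeguards for the endpoint, but they reclassify outcomes and leave the covariate as it is.

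The window might be defined in the separate SAP that the protocol mentions, which is not among the documents available here. However, 8.3.4 and 8.3.7 do not defer this definition, whereas other analyses (8.3.3.6, 8.3.6) explicitly defer their details. The heading of 8.3.3.3 suggests that the sponsor may have meant use within blanking. That is a reason to say so, because the covariate text does not.

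The baseline label is a smaller matter. In 8.3.7 amiodarone sits in an additional list below the one called baseline, so how far the label reaches is arguable.

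**Conclusion.** The point holds as a bias of unknown size. Followed as written, the covariate in 8.3.4 and 8.3.7 overlaps with the PEE and can be caused by it, and both routes move the coefficient toward harm. In the illustrations the apparent OR runs from 1.40 to 2.37 for 5 to 15 late-rescued failures, and from 1.12 to 1.95 for 5% to 30% of users continuing, with a true OR of 1.0 throughout. Apart from the 45% failure rate and the planned 258, the inputs are assumptions.

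The consequence is limited. These are secondary models screened at 0.15, and the primary PEE test and the study success rule do not use them. The definition should still be corrected before analysis, because the coefficient as specified cannot be read as an effect of early amiodarone.

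**What to change.** In both 8.3.4 and 8.3.7:

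1. Define the covariate as amiodarone use at any time from the Index Procedure through the end of the Blanking Period (yes/no). Count subjects whose first use comes later as no use. This removes the late starters.
2. Do not treat it as a baseline covariate. State that it is measured after the procedure and closed before the effectiveness period.
3. Show separately, by covariate group, the failures due to amiodarone use alone. Early users who continue past the allowed period remain failures by definition, and the window does not change that.
4. Report the result as an association. Recurrence during blanking can itself prompt amiodarone, so some confounding by early recurrence remains.

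The cost is a few lines of wording and one extra tabulation. Section 7.4 already has antiarrhythmic drug and dose changes recorded at every follow-up assessment. The change concerns an analysis definition only and alters no treatment rule.
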